Illness narratives will be conducted in the language of preference of the participant by one member of the research team. They will last for approximately one hour. Prior to the activity commencing participants will be approached to take part either in person or through telephone contact. The study will be explained to participants who will have the right to refuse. Information sheets will be shared with participants either verbally or in writing depending on the literacy level and preference of the participant. Participants will be given the opportunity to ask any questions in advance of the activity and the study re-explained prior to the activity commencing. If participants are willing to take part, they will be asked to sign a written consent form or verbal consent taken in the presence of a witness if they are illiterate or unable to sign. As with other methods, participants will be made aware at the outset that they will have the opportunity to be referred to a mental health provider if they feel they need it as a result of workshop participation. All participants will be given the right to withdraw from the study at any time.

Participatory workshops

V1.0 01.04.2025

[figure not shown]
We will conduct a series of participatory workshop with persons affected utilising problem tree analysis and matrix ranking. Workshops will be used to encourage persons affected to identify their main problems experienced which affect mental wellbeing, as well as exploring the underlying root causes and consequences of these. The matrix ranking will assist them in identifying their priority problems and the priority interventions to address these.

For all participatory workshops, participants will initially be approached in person and the study will be explained to them. Information sheets will be shared with participants in advance of the interview either verbally or in writing depending on the literacy level and preference of the participant. Participants will be given the opportunity to ask any questions in advance of the workshop and the study re-explained prior to the activity commencing. If participants are willing to take part, they will be asked to sign a written consent form or verbal consent taken in the presence of a witness if they are illiterate or unable to sign. Participants will be made aware at the outset that they will have the opportunity to be referred to a mental health provider if they feel they need it as a result of workshop participation. All participants will be given the right to withdraw from the study at any time. Each workshop will take no more than 2 hours.

Recruitment and sampling

Qualitative recruitment of participants

The following diagram shows the flow of recruitment of participants for the qualitative components of this study. All information sheets that will be used can be found in our study toolkit.

National level participants:

National level representatives have already been involved in grant development workshops and previous engagements and will be contacted via email or phone by one of our research fellows. Information sheet and consent form will be sent via email, after which the participant will be asked to propose a suitable date and time for a remote or in-person interview. On the day of data collection,

our researcher will go over the information sheet, offer the opportunity for questions, and take informed consent via signature.

District level

We will obtain a letter from relevant regional health directors, to inform district director of our study. After providing approval, the district director will provide the research fellows with contact details for other relevant directorate staff (director MH/PH nurses, data manager). These will be approached via phone to schedule a suitable time for a visit from our research fellow. During the visit, the research fellow will provide a verbal explanation about the study and information sheet and will schedule another appointment for an in-person interview, at least 24 hours later. Written informed consent will be obtained via signature prior to interview.

Health centres:

After they have given permission, district directorates will provide our research fellows with the contact details of the in-charge at selected sub-district health facilities. These will be approached via phone to schedule a suitable time for a visit from our research fellow. During the visit, the research fellow will provide a verbal explanation about the study and information sheet and will schedule another appointment for an in-person interview, at least 24 hours later. The in-charge will also be asked to provide contact details for other facility staff (e.g. MH nurse, PH nurse, etc), for whom the recruitment process will be the same. Written informed consent will be obtained via signature.

Community level (CHPS)

At community level, the District Directorate will also provide contact details for the in-charge of the CHPS facilities, who will put the team in touch with CHWs and CHVs. The study team will visit the CHPS, to speak to the in-charge, CHWs and CHVs. Community groups will be identified through the directorate, CHWs and CHVs. Our research team will make a first approach by visiting the group leaders, together with the CHWs/CHVs. Community leaders (e.g. chiefs) will be identified by the CHPS in-charge, who will be asked to pre-inform the leaders about our study, and who will accompany the study team when making a first approach in person. Persons-affected will be identified through CHWs, CHVs, or through snowballing via other persons affected. The CHW/CHV or person affected will join the research team in making the first approach and introducing the study.

For group/community leaders and persons affected, the rest of the consenting process will be as follows: during a first visit, our research team will verbally explain the study, going over the information sheet. At least 24 hours later, they will return to provide another verbal explanation, the opportunity to ask questions, and obtain informed consent via signature or thumbprint, before proceeding with the interview.

Baseline survey: We will conduct use a census approach to survey the NTD population in the 4 intervention sites (expected n=200). NTD patients will be identified as follows: We will work with the district health directorate to identify health facilities with NTD cases in each intervention district (CHPS and health centres). Where available, we will obtain a list from the district health officer with names and contact numbers of persons affected with NTDs registered in these facilities. We will also visit traditional/faith healers in the vicinity of the selected health facility, to ask if they have any NTD patients under their care. Finally, we will speak to community health workers

attached to the local facility, and, upon completion of the survey, we will ask persons affected if they know of anyone else who is affected by one of the target conditions, to identify any non-registered persons affected via snowballing method. As such, it is expected that our census will contribute to case finding. The number of target health facilities will be expanded until we reach the required sample size; once a health facility is selected, we will complete our census, even if this takes us beyond the required sample size.

The first approach will be made by a research assistant, together with a CHV, who will visit the person affected in the community. The research assistant will verbally explain the purpose of the study and provide an information sheet. If the participant is happy to participate, the research assistant will agree to return the next day, or at a date and time of the participants choosing. On the day of the survey, the research assistant will again explain the purpose of the study, provide an opportunity to ask questions and obtain written informed consent via thumbprint or signature.

Policy brief

The primary purpose of the policy analysis will be to develop an understanding of the policy processes, stakeholders and structures that may impact the development and delivery of the integration of mental health within care for people with NTDs in Ghana. This will inform the research design as well as the way that evidence is synthesised, packaged and disseminated. The policy analysis will primarily focus on national policy.

Documents will be obtained by liaising with stakeholders in the Ministry of Health and Ghana Health Service. Once documents are obtained, we will develop a thematic framework to rapidly extract data from the documents, before synthesising the data from all the reports.

Data Analysis

Analysis will be completed collaboratively between all members of the research team.

Qualitative data

The participatory nature of workshops involved in phase one of this study mean that analysis will be an ongoing process involving study participants. The products of each of the participatory workshops, will each feed into the participatory planning meeting in phase two to allow for informed action planning. To harmonise across activities however, the research team will keep a log of key issues and discussion points from each of the participatory workshops to feed into the participatory planning activities.

For components of participatory workshops phase one, where notes and recordings (with the agreement of participants) are transcribed, these will be analysed thematically using a framework approach as described below³¹. All other qualitative data will also be analysed using this approach.

This thematic analysis will be conducted by the research team and also feed into the participatory planning activities for validation and consideration.

Thematic Framework Approach

Phase 1: Data Management

Step 1: Familiarisation - the analysis team will read and re-read the verbatim transcripts to 'familiarise' themselves with the data. Whilst doing this they take note of key themes emerging.

Step 2: Developing a thematic/coding framework - a framework through which to sort the data will be developed based on original aims and objectives and any inductive themes identified during the familiarisation process.

Step 3: Indexing/coding data - the thematic/coding framework will be applied to all the data. This will be assisted by the use of NVIVO software. If teams are unfamiliar with NVIVO software, training will be provided.

Phase 2: Data Explanation

Step 4: Charting - data will be lifted from its original context based on its allocation to the coding/thematic framework and placed within a chart.

Step 5: Mapping - the final stage of the process will be to interpret, and map the range of polarities and similarities within the data.

Qualitative analysis software NVIVO 12 will be used to support data management and analysis.

Quantitative data

Data will be analysed using R.

At baseline, we will first use the NTD population dataset, to explore our main outcomes (mental health and quality of life of people affected). Using descriptive statistics, we will calculate the prevalence of depression and anxiety and summarise other key variables. The data will be presented separately by sex. We will use inferential statistics (multivariable linear regression analysis) to explore associations between mental health, quality of life, stigma and demographic variables. We will include interaction effects to see if the effect of predictors on our main outcomes differs from sex.

We will also specifically explore the relationship between mental health and time since diagnosis, symptom severity, disability and functioning, using inferential statistics (multivariable linear regression), including interaction terms between key variables and sex.

The endline analysis will include descriptive statistics to summarise outcomes at each time point, stratified by sex. To evaluate changes over time and potential sex differences, we will use linear mixed-effects models with random intercepts for participants. Fixed effects will include time, sex, and a time \times sex interaction term to assess whether the trajectory of mental health outcomes differs between males and females. Model assumptions will be checked, and sensitivity analyses will be conducted as appropriate.

Findings from both qualitative and quantitative analyses will be integrated to provide a holistic understanding of how mental health services can be effectively incorporated into NTD programs. Triangulation of data sources will enhance the reliability and validity of study findings, ensuring that recommendations are evidence-based and actionable.

Dissemination, Outputs and Anticipated Impact

Our approach to impact is guided by our IMAGINE Ghana Theory of Change (Figure1); and which will be regularly reviewed at consortium meetings to reflect any changes in context.

[figure not shown]

Figure 1. Overview of IMAGINE Ghana study phases and work packages

Our impact at the **global level** will be to: Drive advances in the **development and evaluation of interventions and strategies for improved treatment and management of co-occurring NTDs and MHCs within LMICs**.

Our global impact will be accompanied by impact within Ghana at three key levels:

Individual: People affected (and their families) have access to integrated services for the prevention, treatment and management of co-occurring NTDs and MHCs, they experience less stigma and discrimination, and have more opportunity to participate within the life of their community.

Community: Contribute to increasing health literacy related to NTDs and MHCs leading to a reduction in stigma, social exclusion and poverty (through reduced discrimination in social and work spaces).

National: Effective co-ordination collaboration and access to evidence-based information for the provision of an essential care package for co-occurring NTDs and MHCs delivered as part of integrated case management interventions that are embedded within stronger and more responsive health system.

Impacts will be realised through achieving the following **outcomes**:

Outcome 1: Evidence on the most effective, acceptable, affordable, equitable, inclusive and sustainable context-specific community, health and social systems-based interventions for co-occurring NTDs and MHCs integrated into programme strategies by government, regional and international stakeholders.

Outcome 2: Improved capacity among health system and community stakeholders to identify intervention solutions, and to promote a culture of working together to co-produce, implement, assess and adapt interventions to respond to holistic care needs and rights of people affected by co-occurring NTDs and common MHCs.

Systematic inclusion of the needs and priorities of affected persons within the design, delivery, monitoring and evaluation of system-based interventions to ensure equitable management of co-occurring NTDs and common MHCs that meets the needs of vulnerable populations and promotes social inclusion and stigma reduction.

Outcome 3: Evidence on the most effective, acceptable, affordable, equitable, inclusive and sustainable context-specific community, health and social systems-based interventions for co-occurring NTDs and MHCs integrated into programme strategies by government, regional and international stakeholders.

Outcome 4: Improved capacity among health system and community stakeholders to identify intervention solutions, and to promote a culture of working together to co-produce, implement, assess and adapt interventions to respond to holistic care needs and rights of people affected by co-occurring NTDs and common MHCs.

Outcome 5: Established technical and community advisory groups of policy makers, practitioners, researchers, persons affected and other community stakeholders collaborating together, and learning from each other, to identify and implement solutions for the integrated management of NTDs and common MHCs.

Our approach to Engagement, Research Uptake and Maximising Impact

Our approach to research uptake builds on many years' experience of generating policy relevant research in partnership with a range of stakeholders; working directly with program managers and policy makers in the definition of the problem and execution of the research to facilitate rapid uptake of best practices; overcoming barriers to the use of evidence; and applying best practice communications techniques to ensuring that findings are packaged and disseminated to target audiences through a two-way process of dialogue and exchange. We have designed IMAGINE Ghana to maximise impact based on prior experience through REDRESS.

Partners already have strategic platforms for research uptake, with relationships established with persons affected, Ministry of Health Mental Health and NTD programmes, health workers and community actors (e.g. religious leaders or traditional healers). We will engage with digital means of dissemination building on existing networks of persons affected e.g. leprosy patient groups, where these exist. We will engage with key audiences as follows:

With persons affected and community public involvement organisations: We will engage with persons affected through involvement in community advisory board, as co-researchers, during regular participatory workshops and dissemination meetings.

Within government bodies and key stakeholders in Ghana: We will actively communicate through presentations and dialogue at technical review meetings and NTD annual review processes. We will also work with stakeholders such as the NTD ambassador for Ghana, Rev. [name], to reach high-level decision makers; build new platforms and engage with pre-existing coalitions (e.g. National Union(s) of the Disabled); conduct sensitisation meetings with national bodies and supporting their capacity to access, understand and apply research evidence; and participate in national meetings and research forums.

Within the wider LMIC community: We are actively connected to many working groups and networks that are of strategic benefit to the uptake of this work. E.g. NGDO Network on NTDs (NNN) Disease Management, Disability and Inclusion (DMDI) technical working groups, including those which focused on the development of the ECP for NTDs and Mental Health. Members of the IMAGINE GHANA team also serve as members of key bodies to WHO involved in NTD strategy and research, such as WHO Operational Research Working Group on Skin NTDs ([name]). IMAGINE GHANA will also leverage additional formal dissemination channels where there is discussion with the wider LMIC community, for example; COR-NTD, ASTMH, Health Systems Global.

Capacity strengthening

Individual- To meet our capacity and capability strengthening objectives a capacity needs assessment will be carried out followed by working with early career researchers to development plans identifying short, medium and long-term opportunities to develop individual skills against need. Training will be nested in a wider approach to capacity strengthening with the development of individual personal development plans reviewed on an annual basis.

Institutional- we will develop the capacity of all partners and their systems to support the development of research infrastructure for the evaluation of interventions and strategies for improved treatment and management of NTDs and MHCs in Ghana. Plans for areas of strengthening will be established following an institutional needs assessment and planned according to budget.

Given the sensitivity of the issues we are working on, we will focus on generating and sharing lessons from navigating ethical challenges and co-producing and monitoring safeguarding risk assessments and strategies to minimise risk (Mansaray et al, 2022, Aktar et al, 2020). Inclusion will be central within our co-produced safeguarding plans, ensuring that people with disabilities are kept safe and enabled to access reporting mechanisms (e.g. ensuring there is not a single methodology for reporting cases of concern). We also recognise the barriers for many lived experience organisations in participation and will seek to provide organisational support for leadership through the programme to enable them to more consistently be equipped to contribute to IMAGINE GHANA and future programmes.

References

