Narrative Case Study Interviews (20 case studies (5 per district) Person affected leprosy + caregiver Person affected BU + caregiver Person affected LF + caregiver Person affected by cutaneous leishmaniasis + caregiver Person affected by onchocerciasis + caregiver	Narrative Case Study Interviews	What are the syndemic relationships between NTDs, mental health conditions and disability? How applicable are existing intervention approaches from other settings relevant to addressing these interactions in Ghana?

3) Policy analysis of existing programme documents to understand the necessary tools and resources required to facilitate integrated implementation, as well as the current policy context within Ghana relating to NTDs and mental health.

The primary purpose of the policy analysis will be to develop an understanding of the policy processes, stakeholders and structures that may impact the development and delivery of the integration of mental health within care for people with NTDs in Ghana. This will inform the research design as well as the way that evidence is synthesised, packaged and disseminated. The policy analysis will primarily focus on national policy.

Documents will be obtained by liaising with stakeholders in the Ministry of Health and Ghana Health Service. Once documents are obtained, we will develop a thematic framework to rapidly extract data from the documents, before synthesising the data from all the reports.

Baseline survey with persons affected and general population

At this stage, a census approach will be used to survey all persons affected by NTDs in our study sites. The purpose of this survey is to establish the prevalence of mental health conditions amongst persons affected and examine factors associated with reduced mental health/wellbeing; and gather data that will serve as the baseline for our impact evaluation. The survey will consist of tools recommended in the NTD morbidity toolkit, including the PHQ-9, GAD-7, Warwick mental wellbeing scale, to capture our main study outcomes, namely depression, anxiety and wellbeing. We will also use the EQ-5L-5L

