for Quality of Life, Washington Group questionnaire to capture disability, Sari Stigma Scale, and Participation scale, in addition to capturing socio-demographic data (gender, age, education level), disease specific data (NTD type, time since diagnosis, symptom level) and costing questions. Some of these tools have been used previously in our setting; those that have not will be translated and piloted before use.

Participatory intervention design workshops

The final component of phase 1 will be the intervention design workshops, where we will bring together persons affected, key stakeholders from within GHS and MOH and researchers and other key stakeholders e.g. pluralistic providers in a participatory planning workshop. During this workshop findings from phase 1 (policy analysis, health systems readiness assessment, qualitative and participatory research findings) will be presented. Stakeholders will then be asked to reflect on these findings to prioritise and develop interventions to integrated mental health and stigma reduction within care for persons with skin NTDs in Ghana, based on the new and consolidated evidence base. Interventions will draw on global expertise, but will be discussed and reviewed together to ensure these are applicable within the Ghanaian setting.

Phase 2: Implement and monitor phase

This phase will build on the findings from the design phase to introduce a Ghanaian version of the essential care package for NTDs, stigma and mental health. Intervention design and delivery will draw on evidence and expertise. MOH actors will provide technical support during this research phase to ensure interventions developed are feasible and sustainable within routine health systems operations, as well as being aligned to the funding cycles for the NTD programme. This will be led by the national programme, with interventions leveraging on existing programme plans (e.g. updating training materials to include a focus on psychosocial support to be rolled out in routine activities). We will bring together persons affected, health systems stakeholders, researchers and collaborators in a participatory design workshop. This workshop will also engage additional community and health systems stakeholders identified as critical during the design phase and through stakeholder mapping activities linked to the adaption and adoption of final interventions.

Phase 3: Evaluate phase

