This phase will involve a multi-disciplinary evaluation of the intervention bundle to make recommendations for future delivery of an essential care package for co-occurring NTDs and MHCs. The details of the evaluate phase will be determined following development of the intervention, and so the methods included in table 2 are provisional for now, and may be adjusted and updated in the amendment to be submitted once details on the intervention are known. Participant numbers for these methods have not yet been estimated and will be included in the subsequent amendment.

Our evaluation takes a realist theory-based approach and is concerned with understanding; what components of our intervention bundle are effective, with which implementation strategies, for whom, in what settings and for how long (Holtrop et al, 2021). We are focused on understanding the impact of the different dimensions of our intervention bundle and the contexts in which they are and

are not effective. Our multi-disciplinary evaluation will be guided by the RE-AIM framework (Holtrop et al, 2021). The RE-AIM framework consists of five core domains that are designed to be considered at different implementation levels from the perspective of different stakeholders: **Reach** and **Effectiveness** (Individual level); **Adoption** and **Implementation** (facility, system and policy level); and **Maintenance** (all levels) (Holtrop et al, 2021).

A range of qualitative methods will be used to evaluate the intervention alongside the quantitative aspects.

The quantitative aspect of the evaluation will consist of a longitudinal cohort study with repeated measures at baseline and 12 months after the start of intervention, to track individual level changes and do an initial assessment of sustainability of the intervention. We will track engagement with the intervention via an 'intervention passport', in which persons affected will collect stamps/stickers for every engagement with the health system in relation to their NTD/Mental Health condition. The evaluation will also include a cost-consequence and cost-effectiveness analysis.

Phase 4: Adjust phase

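### Does it matter that quality of life is an additional measure in the baseline survey section but a main outcome in the analysis section?

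*Protocol*

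**What the plan says.** In the Protocol, under *Baseline survey with persons affected and general population* (Phase 1), three scales are included "to capture our main study outcomes, namely depression, anxiety and wellbeing". The next sentence begins "We will also use the EQ-5L-5L" and continues "for Quality of Life, Washington Group questionnaire to capture disability, Sari Stigma Scale, and Participation scale". The same section says the survey will "gather data that will serve as the baseline for our impact evaluation".

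Under *Phase 3: Evaluate phase*, the quantitative evaluation is a "longitudinal cohort study with repeated measures at baseline and 12 months after the start of intervention". That section also says that the details of this phase will be settled once the intervention has been developed, and that an amendment will follow.

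Under *Data Analysis, Quantitative data*, the baseline analysis uses the survey "to explore our main outcomes (mental health and quality of life of people affected"). It then describes multivariable linear regression relating mental health, quality of life, stigma and demographic variables, with interactions by sex for the main outcomes. For the endline it says: "The endline analysis will include descriptive statistics to summarise outcomes at each time point, stratified by sex". Linear mixed-effects models follow, with a time-by-sex term "to assess whether the trajectory of mental health outcomes differs between males and females".

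**The concern.** The survey section appears to close its list of main outcomes at three, and quality of life falls outside it, beside disability, stigma and participation. The analysis section puts quality of life inside. Both are current text, so a statistical analysis plan could follow one only by departing from the other.

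The difference could carry into the evaluation, because the survey supplies its baseline. The endline paragraph does not name quality of life, and the only outcomes it names for the mixed model are mental health outcomes. A reader could therefore ask whether the 12-month change in quality of life is a main result, and whether it is modelled at all. If the rank stayed open until results were known, quality of life could be moved up or down according to how it turned out.

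**Working it through.** The protocol states no figure on this point. The check is a comparison of the text and a count of instruments.

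**1. Instruments in the survey section.** PHQ-9, GAD-7, Warwick scale, the quality-of-life tool, the Washington Group questionnaire, the Sari Stigma Scale and the Participation scale make 7. The survey section calls 3 of them main, which leaves 7 − 3 = 4 additional.

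**2. The same instruments under the analysis section.** That section names concepts where it lists the main outcomes, not instruments, so the count depends on what mental health covers.

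| Reading of mental health | Main | Additional | Instruments whose label differs from the survey section |
|---|---|---|---|
| Depression, anxiety and wellbeing | 3 + 1 = 4 | 7 − 4 = 3 | 1 (quality of life) |
| Depression and anxiety only | 2 + 1 = 3 | 7 − 3 = 4 | 2 (quality of life and wellbeing) |

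The first reading is natural, since a wellbeing scale fits easily under mental health. The second has some support, because the analysis section mentions only depression and anxiety when it turns to prevalence. On both readings quality of life changes label. It cannot be absorbed into wellbeing, because it has its own instrument and is listed separately from mental health in the regression.

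**3. What depends on the label at baseline.** Quality of life is named in the baseline regression whichever label it carries. The sex interactions are planned for the main outcomes, but that sentence stands in the same paragraph that has just said what the main outcomes are. An analyst working from that paragraph has a definition to hand, and it includes quality of life.

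**4. What depends on the label at endline.** The descriptive summaries cover outcomes at each time point without restriction, and the mixed models are introduced for changes over time, again without restriction. The phrase about mental health outcomes occurs only in the clause explaining the purpose of the time-by-sex term. It does not limit which scales are modelled for change. Quality of life fits within this text without contradiction.

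**5. What depends on the label for inference.** The protocol sets no significance level, power calculation, multiplicity adjustment, primary and secondary hierarchy or success criterion for these scales. The evaluation follows a single cohort measured at two times. No decision in the document is reached differently with 3 main outcomes than with 4.

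**The case for a change.** The strongest argument for acting is that this is a contradiction and not an omission. Both statements sit in baseline text that is not marked provisional, so neither an unseen analysis plan nor the deferral of evaluation details excuses it. The repair would cost a few words in an amendment that is already planned, and one list fixed before endline analysis would remove any room for choosing the rank after seeing results.

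Part of this stands. The wording is inconsistent, and the deferral does not reach the baseline sentences. But the deferral does cover the evaluation broadly, and which outcomes are main at 12 months is naturally one of its details. Which scales enter the mixed model is commonly left to the analysis plan. The endline point is therefore a consequence of the wording difference and not a separate defect.

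The risk of selective emphasis is possible in principle, but it is weak here. All scales are collected, the endline summaries are not limited to main outcomes, and no claim of success is attached to the label. Harmonising the wording would also leave the rank of quality of life to the sponsor, so it would not by itself alter any analysis.

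**Conclusion.** The inconsistency is real, but no change to the plan is called for. It affects the label of one instrument out of seven, or two on the narrower reading of mental health. It changes no data collected, no estimate and no conclusion that the protocol sets out to draw. An analyst can follow the analysis section, which defines its own main outcomes, and report quality of life at both time points alongside the other scales. If the sponsor wants to align the two sentences, the planned evaluate-phase amendment is a convenient place, but nothing depends on it.

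This rests on two assumptions: that the survey scales are repeated at 12 months, as the repeated-measures design implies, and that no later document attaches a decision rule to the main outcomes without first listing them.
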